#### C.6.10.1 Secondary Endpoints Tested to Support Labeling Claims

The following secondary endpoints will be tested, in order, to support labeling claims:

1. Transvalvular mean gradient at 12 months (non-inferiority): TAVI vs. SAVR (secondary objective #12). The hypothesis of interest is

$$H: \mu_{TAVI} < \mu_{SAVR} + 5$$

where  $\mu_{TAVI}$  and  $\mu_{SAVR}$  denote the average mean gradient from at 12 months, measured in mmHg. This objective will be evaluated using a Bayesian version of a two-sample t-test (see Section C.11). The posterior probability  $P(H | \text{data})$  will be calculated and compared to a threshold of 0.95.

2. Effective orifice area at 12 months (non-inferiority): TAVI vs. SAVR (secondary objective #12). The hypothesis of interest is

$$H: \mu_{TAVI} > \mu_{SAVR} - 0.1$$

where  $\mu_{TAVI}$  and  $\mu_{SAVR}$  denote the mean effective orifice area at 12 months, measured in  $\text{cm}^2$ . This objective will be evaluated using a Bayesian version of a two-sample t-test (see Section C.11). The posterior probability  $P(H | \text{data})$  will be calculated and compared to a threshold of 0.95.

3. Change in NYHA classification from baseline to 12 months (non-inferiority): TAVI vs. SAVR (secondary objective #8). The hypothesis of interest is

$$H: \mu_{TAVI} > \mu_{SAVR} - 0.375$$

where  $\mu_{TAVI}$  and  $\mu_{SAVR}$  denote the mean number of classification improvements in NYHA from baseline to 12 months. For subjects with NYHA categories at both baseline and 12

month visit, the NYHA classification improvements will be calculated as  $NYHA_{baseline} - NYHA_{12month}$ . This objective will be evaluated using a Bayesian version of a two-sample t-test (see Section C.11). The posterior probability  $P(H | data)$  will be calculated and compared to a threshold of 0.95.

4. Change in Kansas City Cardiomyopathy Questionnaire (KCCQ) score from baseline to 30 days (non-inferiority): TAVI vs. SAVR (secondary objective #11). The hypothesis of interest is

$$H: \mu_{TAVI} > \mu_{SAVR} - 5$$

where  $\mu_{TAVI}$  and  $\mu_{SAVR}$  denote the mean improvements in the KCCQ score from baseline to 30 days. For subjects with KCCQ score at both baseline and 30 days, the improvement in KCCQ will be calculated as  $KCCQ_{30day} - KCCQ_{baseline}$ . This objective will be evaluated using a Bayesian version of a two-sample t-test (see Section C.11). The posterior probability  $P(H | data)$  will be calculated and compared to a threshold of 0.95.

5. Length of index procedure hospital stay after TAVI vs. SAVR (secondary objective #18). The hypothesis of interest is

$$H: \mu_{TAVI} < \mu_{SAVR}$$

where  $\mu_{TAVI}$  and  $\mu_{SAVR}$  denote the mean length of index hospital stay. This objective will be evaluated using a Bayesian version of a two-sample t-test (see Section C.11). The posterior probability  $P(H | data)$  will be calculated and compared to a threshold of 0.975.

6. Transvalvular mean gradient at 12 months (superiority): TAVI vs. SAVR (secondary objective #12). The hypothesis of interest is

$$H: \mu_{TAVI} < \mu_{SAVR}$$

where  $\mu_{TAVI}$  and  $\mu_{SAVR}$  denote the average mean gradient from at 12 months, measured in mmHg. This objective will be evaluated using a Bayesian version of a two-sample t-test (see Section C.11). The posterior probability  $P(H | data)$  will be calculated and compared to a threshold of 0.975.

7. Effective orifice area at 12 months (superiority): TAVI vs. SAVR (secondary objective #12). The hypothesis of interest is

$$H: \mu_{TAVI} > \mu_{SAVR}$$

where  $\mu_{TAVI}$  and  $\mu_{SAVR}$  denote the mean effective orifice area at 12 months, measured in  $cm^2$ . This objective will be evaluated using a Bayesian version of a two-sample t-test (see Section C.11). The posterior probability  $P(H | data)$  will be calculated and compared to a threshold of 0.975.

8. Change in Kansas City Cardiomyopathy Questionnaire (KCCQ) score from baseline to 30 days (superiority): TAVI vs. SAVR (secondary objective #11). The hypothesis of interest is

$$H: \mu_{TAVI} > \mu_{SAVR}$$

where  $\mu_{TAVI}$  and  $\mu_{SAVR}$  denote the mean improvements in the KCCQ score from baseline to 30 days. For subjects with KCCQ score at both baseline and 30 days, the improvement in KCCQ will be calculated as  $KCCQ_{30day} - KCCQ_{baseline}$ . This objective will be evaluated using a Bayesian version of a two-sample t-test (see Section C.11). The posterior probability  $P(H | data)$  will be calculated and compared to a threshold of 0.975.

9. Days alive out of the hospital at 12 months after TAVI vs. SAVR (secondary objective #10). The hypothesis of interest is

$$H: \mu_{TAVI} > \mu_{SAVR}$$

where  $\mu_{TAVI}$  and  $\mu_{SAVR}$  denote the mean number of days alive out of the hospital at 12 months. This objective will be evaluated using a Bayesian version of a two-sample t-test (see Section C.11). The posterior probability  $P(H | data)$  will be calculated and compared to a threshold of 0.975.

10. Days alive out of the hospital at 24 months after TAVI vs. SAVR (secondary objective #10). The hypothesis of interest is

$$H: \mu_{TAVI} > \mu_{SAVR}$$

where  $\mu_{TAVI}$  and  $\mu_{SAVR}$  denote the mean number of days alive out of the hospital at 24 months. This objective will be evaluated using a Bayesian version of a two-sample t-test (see Section C.11). The posterior probability  $P(H | \text{data})$  will be calculated and compared to a threshold of 0.975.

11. Change in SF-36 Physical Summary Scale from baseline to 3 months: TAVI vs. SAVR (secondary objective #11). The hypothesis of interest is

$$H: \mu_{TAVI} > \mu_{SAVR}$$

where  $\mu_{TAVI}$  and  $\mu_{SAVR}$  denote the mean improvements in the SF-36 Physical Summary Scale from baseline to 3 months. This objective will be evaluated using a Bayesian version of a two-sample t-test (see Section C.11). The posterior probability  $P(H | \text{data})$  will be calculated and compared to a threshold of 0.975.

12. Change in EQ-5D from baseline to 3 months: TAVI vs. SAVR (secondary objective #11). The hypothesis of interest is

$$H: \mu_{TAVI} > \mu_{SAVR}$$

where  $\mu_{TAVI}$  and  $\mu_{SAVR}$  denote the mean improvements in the EQ-5D from baseline to 3 months. This objective will be evaluated using a Bayesian version of a two-sample t-test (see Section C.11). The posterior probability  $P(H | \text{data})$  will be calculated and compared to a threshold of 0.975.

13. Incidence of MACCE at 30 days or hospital discharge, whichever is longer: TAVI vs. SAVR (secondary objective #1). The hypothesis of interest is

$$H: \pi_{TAVI} < \pi_{SAVR}$$

where  $\pi_{TAVI}$  and  $\pi_{SAVR}$  denote the binary rate of MACCE at 30 days or hospital discharge (if longer). The posterior probability  $P(H | \text{data})$  will be calculated and compared to a threshold of 0.975. The statistical method will be the Bayesian version of a comparison of proportions (see Section C.11).

14. Incidence of major vascular complications at 30 days or hospital discharge, whichever is longer: TAVI vs. SAVR (secondary objective #3). The hypothesis of interest is

$$H: \pi_{TAVI} < \pi_{SAVR}$$

where  $\pi_{TAVI}$  and  $\pi_{SAVR}$  denote the binary rate of major vascular complications at 30 days or hospital discharge (if longer). The posterior probability  $P(H | \text{data})$  will be calculated and compared to a threshold of 0.975. The statistical method will be the Bayesian version of a comparison of proportions (see Section C.11).

15. Incidence of major or life-threatening bleeding event at 30 days or hospital discharge, whichever is longer: TAVI vs. SAVR (secondary objective #3). The hypothesis of interest is

$$H: \pi_{TAVI} < \pi_{SAVR}$$

where  $\pi_{TAVI}$  and  $\pi_{SAVR}$  denote the binary rate of major or life-threatening bleeding events at 30 days or hospital discharge (if longer). The posterior probability  $P(H | \text{data})$  will be calculated and compared to a threshold of 0.975. The statistical method will be the Bayesian version of a comparison of proportions (see Section C.11).

16. Incidence of all strokes at 30 days or hospital discharge, whichever is longer: TAVI vs. SAVR (secondary objective #15). The hypothesis of interest is

$$H: \pi_{TAVI} < \pi_{SAVR}$$

where  $\pi_{TAVI}$  and  $\pi_{SAVR}$  denote the binary rate of strokes at 30 days or hospital discharge (if longer). The posterior probability  $P(H | \text{data})$  will be calculated and compared to a threshold of 0.975. The statistical method will be the Bayesian version of a comparison of proportions (see Section C.11).

17. Incidence of moderate/severe aortic insufficiency after TAVI vs. SAVR (secondary objective #12). The hypothesis of interest is

$$H: \pi_{TAVI} < \pi_{SAVR}$$

where  $\pi_{TAVI}$  and  $\pi_{SAVR}$  denote the proportion of subjects with moderate/severe aortic insufficiency at the discharge echo. The posterior probability  $P(H | \text{data})$  will be calculated and compared to a threshold of 0.975. The statistical method will be the Bayesian version of a comparison of proportions (see Section C.11).

18. New pacemaker implant rate for TAVI at 30 days or hospital discharge, whichever is longer (secondary objective #7). The hypothesis of interest is

$$H: \pi_{TAVI} < 30\%$$

where  $\pi_{TAVI}$  denote the binary rate of new pacemaker implants for TAVI at 30 days or hospital the discharge (if longer). The posterior probability  $P(H | \text{data})$  will be calculated and compared to a threshold of 0.975. The statistical method will be the Bayesian version of a comparison of proportions (see Section C.11).

Other than the hierarchical testing procedure described above, no further multiplicity adjustments will be made in the analyses of the secondary endpoints. Summary data from other secondary objectives, such as device success and procedural success from secondary objectives #20 and #21, respectively, may be provided in the device labeling. However, no claims of statistical significance or other statistical inference will be made.

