Physicians' preferences for lesser invasive strategies have fuelled the ongoing interest in developing minimally invasive transcatheter therapies. Alain Cribier pioneered the transcatheter aortic valve implantation (TAVI) technology and reported the first-in-man experience of TAVI in a patient with symptomatic AS who was deemed inoperable in 2002(10). Subsequent feasibility studies validated the proof of concept (11, 12). The Edwards-SAPIEN valve (Edwards Lifesciences, Irvine, CA, USA) and the Medtronic CoreValve system (Medtronic Corporation, Minneapolis, MN, USA) were the first two TAVI platforms with CE mark approval, followed by the Symetis Acurate (Symetis, Ecublens, Switzerland) and JenaValve (JenaValve, Munich, Germany). Numerous single-center and multi-center observational registries followed suggesting the safety and performance of the TAVI technology (13-17). The TAVI technology comes with its own specific complications (18), not necessarily overlapping with those of SAVR: vascular injury; stroke, cardiac injury such as heart block, coronary obstruction, and cardiac perforation; paravalvular leak; and valve misplacement. The non-uniformity in presenting respective data makes a comparison of results from different centers challenging (19, 20). The Valvular Academic Research Consortium (VARC), a FDA-endorsed collaboration between academic research organizations and professional societies in the United States and Europe is an initiative to generate a consensus statement on TAVI related definitions aiming to create order and uniformity making data more prone to analysis and comparison (21, 22).

Technical refinements and commercial entrepreneurship have made the technology accessible to many centers worldwide. This might pose future implications since few randomized trials with TAVI have been performed.

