    - Assessment should include aortic valve function, central or paravalvular leakage, valve gradient, exclude remaining LVOTO from subvalvular stenosis as well as ventricular function with special emphasis on new segmental wall function abnormalities.
    - Any regurgitation of more than trace should be critically evaluated and at surgeon's discretion the valve re-inspected and if necessary changed.

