#### Sample Size Justification

The assumed values  $\pi_T = \pi_C = 0.17$  are based on the data published by Iturra et al and CoreValve US Pivotal High Risk study results. As reported in the Iturra paper, the incidence of all-cause mortality at 30 days was 2.8% and the late all-cause mortality Kaplan-Meier rate at 24 months was 12.1%. The overall 24-month all-cause mortality rate was approximately 15%. STS score reported in the Iturra paper ( $5.6 \pm 1.1$ , n=502) was similar to the STS score for subjects currently enrolled in the SURTAVI study ( $5.6 \pm 1.4$ , n=654), and it is believed that the 24-month all-cause mortality rate in SURTAVI will be approximately 15% at 24 months. The major stroke rate was 3.2% for subjects who survived to 1 year in the CoreValve Pivotal High Risk study. The High Risk study enrolled a higher-risk population than SURTAVI, therefore, the major stroke rate in the High Risk study is adjusted downward, and it is believed the disabling stroke rate at 24 months would be approximately 2% in the SURTAVI study. Overall, the estimation of the all-cause mortality or disabling stroke rate at 24 months is 17%.

Although the pre-specified analysis methods are Bayesian, the sample size is guided by a standard frequentist non-inferiority power analysis. Under the assumptions of  $\pi_T = \pi_C = 0.17$ , non-inferiority margin  $\delta=0.07$ , 1:1 randomization,  $\alpha= 0.05$ , and power = 95%, the method of Farrington and Manning as implemented in PASS 2008 indicates that the required sample size for a single-look analysis is 1258. To allow for up to 6% dropout, 1339 subjects must be accrued. Furthermore, to compensate for power lost in a two-look group sequential analysis plan using Pocock-type alpha spending, the sample size would have to be increased by about 12.5%. This leads to an estimated sample size of 1531. Thus a sample size of 1600 mITT subjects should provide ample power for establishing non-inferiority in the primary hypothesis test.

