### C.6.10 Multiplicity Considerations

It is recognized that with a multiplicity of tests comes inflation in the chance of a false finding of superiority or non-inferiority. Therefore, for the purpose of seeking approved labeling claims on designated secondary objectives, the following standard will be used: If the primary objective demonstrates non-inferiority, claims will be sought for selected secondary non-inferiority and superiority objectives and for superiority on the primary objective metric. These will be tested via a hierarchical (sequential) testing order that preserves the overall study-wise type I error rate at the level of 0.05, while requiring all non-inferiority tests to meet a nominal type I error rate of 0.05 and all superiority tests to meet a nominal type I error rate of 0.025. The testing order is specified below. The following objectives are tested in order, and testing continues if and only if all previous objectives have met their designated success criterion.

1. Primary endpoint (non-inferiority)

2. Transvalvular mean gradient at 12 months (non-inferiority)
3. Effective orifice area at 12 months (non-inferiority)
4. Change in NYHA classification from baseline to 12 months (non-inferiority)
5. Change in KCCQ score from baseline to 30 days (non-inferiority)

All of the above are non-inferiority tests and are tested with a type I error standard of 0.05. If all of the above tests meet their success criterion, the type I error rate of 0.05 that is passed on from the above tests will be split equally (using a Bonferroni justification) between the following parallel subfamilies, so that each subfamily is tested using a type I error rate of 0.025:

Subfamily #1: Primary endpoint (superiority)

Subfamily #2: Secondary (superiority) objectives #5–#18 as enumerated below, tested in ordered sequence such that all  $\alpha$  is passed on to subsequent tests if a test criterion is met, while all testing stops if a test criterion is not met. This procedure controls the type I error rate of this subfamily at the level 0.025.

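### Bleeding, stroke and pacemaker labeling claims can be tested only after TAVI beats surgery on major vascular complications, a gate the protocol neither powers nor justifies

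*Combined protocol and SAP*

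**What the plan says.** Item numbers below are those of C.6.10.1.

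Under C.6.10, once the non-inferiority tests succeed, Subfamily #2 receives a type I error rate of 0.025. It runs through items 5 to 18 in order: alpha passes on after each success, "while all testing stops if a test criterion is not met". For claims, each of these items is evaluated once, when primary non-inferiority is established.

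The last six items are MACCE (13), major vascular complications (14), major or life-threatening bleeding (15), all stroke (16), moderate/severe aortic insufficiency at the discharge echo (17) and new pacemaker below 30% with TAVI (18). Item 14 reads "Incidence of major vascular complications at 30 days or hospital discharge, whichever is longer: TAVI vs. SAVR (secondary objective #3") and item 17 reads "Incidence of moderate/severe aortic insufficiency after TAVI vs. SAVR (secondary objective #12"). Both require a posterior probability above 0.975 that the TAVI rate is lower than the SAVR rate.

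On what to expect for these two outcomes, B.1 says: "The TAVI technology comes with its own specific complications (18), not necessarily overlapping with those of SAVR: vascular injury". The same list goes on to include stroke, heart block and paravalvular leak. For surgery, the intraoperative echo step in C.4.7.2 adds: "Any regurgitation of more than trace should be critically evaluated and at surgeon's discretion the valve re-inspected and if necessary changed".

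**The concern.** In a fixed sequence, a test placed early should be one the trial has a good chance of passing, or one important enough to justify putting everything behind it at risk. The protocol makes neither case for items 14 and 17.

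Its own text gives grounds to doubt a TAVI advantage on item 14. Vascular injury heads the list in B.1. C.4.7.1 places an 18Fr sheath in the primary access artery, whereas C.4.7.2 normally returns arterial blood through the ascending aorta. Much of the definition of a major vascular complication in O.2 concerns access-related injury. D.2 names neither fewer vascular complications nor less regurgitation among TAVI's potential benefits.

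At stake are the labeling claims for bleeding, stroke and pacemaker. Under the present order they can be lost because of a different outcome placed ahead of them, whatever their own data show.

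**Working it through.** **The plan's own figure.** The sample size justification in C.6.5.2 states "the estimation of the all-cause mortality or disabling stroke rate at 24 months is 17"%, used for both arms, with margin 0.07, alpha 0.05 and power 95%. The Farrington-Manning restricted estimates are 0.2105 and 0.1405, so

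n per arm = [1.645·√(0.2105·0.7895 + 0.1405·0.8595) + 1.645·√(2·0.17·0.83)]² / 0.07² = 628.6,

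which rounds up to 629 per arm, 1258 in total. This matches the plan, with alpha read as one-sided. Then 1258/0.94 gives 1339 and 1339/0.875 gives 1531, also as stated. The sample size is therefore sound for the primary endpoint. No corresponding calculation is given for items 14 to 18.

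**Inputs for items 14 to 18.**
- 1600 mITT subjects (C.6.5.2), so about 800 per arm.
- Threshold 0.975 (C.6.10.1).
- Beta(1,1) priors. The protocol states these for the primary endpoint; I assume them here.
- Event rates are assumed over a range, because the documents give none.
- Items 5 to 13 are taken as passed.

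**Method.** With x events in 800, the posterior is Beta(1+x, 801−x). For each SAVR count x_C, let k(x_C) be the largest TAVI count with Pr(π_TAVI < π_SAVR | data) > 0.975. Then

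P(pass) = Σ Bin(x_C; 800, p_C) · Pr[Bin(800, p_T) ≤ k(x_C)], summed over x_C.

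For example, 16 SAVR events (2%) allow at most 6 TAVI events, 24 allow 12, and 40 allow 24.

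**Item 14.**

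| SAVR rate | TAVI equal | TAVI one point higher | TAVI half |
|---|---|---|---|
| 1% | 2.2% | 0.01% | not run |
| 2% | 2.3% | 0.06% | 36% |
| 3% | 2.4% | 0.11% | 52% |
| 4% | 2.4% | 0.17% | 65% |
| 5% | 2.4% | 0.22% | 76% |

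With 700 per arm the three ranges are 2.2 to 2.5%, 0.02 to 0.27%, and 33 to 70%.

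**Item 17.** The same table applies at the same rates. If the SAVR rate is very low, the test has little room to succeed: with no TAVI cases at all, at least 5 SAVR cases are needed. At a SAVR rate of 0.25% that happens 5% of the time.

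**Gated claims tested alone (800 per arm, assumed effects).**
- Bleeding, 15% vs 10%: 85.9%.
- Stroke, 6% vs 3%: 83.1%.
- Pacemaker: passes with at most 214/800 (26.75%); 88.1% if the true rate is 25%.

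**Effect of order.** Take these effects, items 14 and 17 both at 2% in each arm, and independent tests.
- Present order: through bleeding 0.0232 × 0.859 = 2.0%; through stroke × 0.831 = 1.7%; through pacemaker × 0.0232 × 0.881 = 0.03%.
- Items 14 and 17 last: through bleeding 85.9%; bleeding and stroke 0.859 × 0.831 = 71.4%; bleeding, stroke and pacemaker × 0.881 = 62.9%.

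**The case against.** A reader might infer that the sequence is bound to stop at items 14 and 17 almost whatever the data show. The documents do not support that, for four reasons.

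- They give no rate for either outcome, and the sentence in B.1 is qualitative and hedged.
- The O.2 definition of a major vascular complication also covers aortic dissection, aortic or annular rupture and left ventricular perforation, which can occur in either arm. Item 17 counts all moderate/severe insufficiency, not only paravalvular leak. The surgical re-inspection is discretionary, and the TAVI procedure also includes a post-implant aortogram and ballooning as needed. A SAVR rate near zero is therefore not established.
- If TAVI halves a surgical vascular rate of 3% or more, item 14 passes more often than not.
- Item 17 follows bleeding and stroke, so it can block only the pacemaker claim.

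The other side has further fair points. Stroke is on the same list in B.1, so the argument also bears on item 16 standing ahead of item 18, and on MACCE (13), which includes stroke. Nine superiority tests (5 to 13) must pass before any of this matters. The order of claims is a legitimate choice for sponsor and regulator. C.6.5.2 defers detail to the SAP, and the text available to me is one of four parts, so a rationale may exist elsewhere. Finally, the trial is open-label and the sponsor's statisticians analyse it, so a late reordering could look data-driven.

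These points limit the finding but do not remove it. None gives a reason to keep item 14 ahead of bleeding, stroke and pacemaker.

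**Conclusion.** The concern holds as a weakness in ordering, not as an error in inference. Item 14 gates claims 15, 16 and 18, and item 17 adds a second gate for 18 only. If TAVI is no better than surgery on major vascular complications, the chance of going on is at most about 2.5%, and under 0.3% if TAVI is one point worse at SAVR rates of 1 to 5%. If TAVI halves a rate of 2 to 5%, it is 36 to 76%. Claims with about 83 to 88% power of their own would sit behind that gate.

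These figures rest on assumed rates and effects, Beta(1,1) priors, 800 per arm, and success on items 5 to 13; the order comparison also assumes independent tests. The loss is confined to labeling claims: the gated outcomes would still be analysed and reported without a claim (C.6.8.1, C.6.10). Type I error control, the primary endpoint and claims 1 to 13 are untouched. I rate this a low-cost improvement worth making.

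**What to change.** Amend C.6.10.1, and any matching text in C.6.10 and the SAP, so that items 14 and 17 come last in Subfamily #2. The tail becomes 13, 15, 18, 16, 14, 17, or 13, 15, 16, 18, 14, 17 if stroke is given priority over pacemaker. Hypotheses, the 0.975 thresholds and the 0.025 allocation stay as they are; a pre-specified fixed sequence controls the error rate in any order. State the expected rates and the reason for the chosen order.

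Make the change before any unblinded comparative look, and document that it was made independently of accruing data, because the trial is open-label. If the sponsor prefers the present order, the minimum is a stated rationale with assumed rates and power for items 14 and 17.

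The cost is a wording amendment and regulator notification, with no extra subjects, data or alpha. The price falls on claims 14 and 17, which would be tested only if the others succeed. For example, if TAVI halves a 4% vascular rate, claim 14 passes 65% of the time in its present place and about 0.65 × 0.629 = 41% after the move, under the illustrative effects above.
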